Exploratory aim. Examine the relationship between NPS and the coherence between structural and functional aspects of the NPS-shared neural circuit. Cumulative literature suggests that white matter (WM) tracts play a critical role in supporting and shaping brain function.¹³ It is often assumed that FC is dependent on underlying anatomical connections,¹³⁻¹⁵ with decreases in WM integrity in dementia related to reduced functional efficiency.¹⁶ The magnitude of correlation between the structural and functional aspects of NPS-shared neural circuit may implicate the severity of NPS. Here, we will collect diffusion tensor imaging (DTI) at baseline, as part of MRI data acquisition, and examine whether the effects of tDCS on NPS-shared neural circuit and study partner-rated NPS depend on WM integrity. Exploring this question will provide broaden our mechanistic understanding of NPS.

We propose that probing the LPG via tDCS provides a way to experimentally test the causal relationship between our previously discovered NPS-shared neural circuit and study partner-rated NPS. The proposed research is highly innovative, while scientifically grounded, for targeting one brain region that may affect multiple NPS. Validating the hypotheses has the potential to support a future R01 study that directly conducts a Stage 2 trial addressing NPS in MCI or AD, thus ultimately improving patients' quality of life and reducing the caregiver burden.

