17. DATA ANALYSIS PLAN

This is a pilot study for mechanistic understanding of the relationship between our previously discovered NPS-shared neural circuit and study partner-rated NPS. Results from the study will provide information for accurately calculating effect size for future clinical trial. Regardless, in addition to follow the rule of 12-20 subjects per group for a pilot clinical trial, we will calculate the sample size. The sample size calculation is based on the effect size of LPG related tDCS on visual attention performance ($f = 0.45$, $n = 36$). Additionally, the effect size of correlation between NPS-shared neural circuit and patient-report NPI-Q was $r^2 = 0.70$ in our previous study³ – here we use a much more conservative estimation at $r^2 = 0.20$, the sample size will be $n = 37$. All of these calculations are based on power at 0.80 and alpha at 0.05. For an 8-week follow up, we estimate 10% attrition rate. Therefore, we propose a total of 40 intervention subjects for the study.

Aim 1. Determine the effect of tDCS on NPS-shared neural circuit. H: After intervention, the active, relative to sham group will have greater increase in LPG activity, indexed by greater activation in LPG in response to visual attention task (H1a) and greater increase in resting FC strength between LPG and other regions within the NPS-shared neural circuit (H1b). To assess the activation pattern in LPG, we will conduct GLM analysis with the SPM software. The coefficients of GLM corresponding to LPG will be analyzed through hypothesis testing. We will first conduct a simple t-test to evaluate whether the intervention increases LPG activation for each group (at 4 or 8 weeks), and then a more powerful two sample kernel test will be used to test activations distribution difference between groups.⁵¹ Similarly, we will take the FCs between LPG and other regions as a multivariate covariate and apply the two-sample kernel test to evaluate group difference in the change of LPG FC pattern after intervention (at 4 or 8 weeks). In addition, simple multiple testing for each connection will be used as a screening procedure to identify a subset of connections included in the kernel test.

Aim 2. Determine the relationship between NPS-shared neural circuit and study partner-report NPS.

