Exploratory aim. Examine the relationship between (a) NPS and (b) the coherence between structural and functional aspects of the NPS-shared neural circuit. We will conduct a connectome-based analysis to find structural connections that are unique to severity of NPI. The TN-PCA method⁵³ will be used to correlate with severity of NPI. We can replace the high dimensional tensor network summarizing an individual's brain connectome with a K-dimensional vector of brain PC scores; these scores can be used for visualizing variation among individuals in their brain connectomes and in statistical analyses studying relationships between structural and functional aspects of NPS-shared circuit and covariates. We will compare similarities of involved brain regions of NPS circuit for FC and WM across the entire sample at baseline. Quantitatively, we will use the Dice similarity coefficient to evaluate the percentage of overlapped regions. **To examine whether tDCS' effects on NPS-shared neural circuit and study partner-rated NPS depend on baseline WM integrity,** first we will compare the correlations between FC (at different time points) and baseline WM integrity on the overlapped regions between active vs. sham tDCS groups. We expect to see a higher correlation between FC and WM in active group in later time points. Next, using SVR described earlier⁵² we will examine the relationship between the sample's features (baseline WM tracts) and outcome (change of NPI severity or frequency scores).

Blood analysis plan: We will compare AD pathology markers from blood with changes of NPS, cognitive measures, and MRI data using correlational analyses. We will also examine if individuals with positive AD pathology respond differently to tDCS compared to those with negative AD pathology using ANOVA.

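### Comparing FC–WM correlations between arms does not directly estimate whether the tDCS effect on the circuit depends on baseline white matter; a baseline-adjusted arm × WM term would

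*Combined protocol and SAP*

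**What the plan says.** Section 1 (exploratory aim) says the study will "examine whether the effects of tDCS on NPS-shared neural circuit and study partner-rated NPS depend on WM integrity", and Section 17 repeats the question: "whether tDCS' effects on NPS-shared neural circuit and study partner-rated NPS depend on baseline WM integrity". White matter is measured once: "we will collect diffusion tensor imaging (DTI) at baseline".

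Section 17 gives two steps. For the circuit, "we will compare the correlations between FC (at different time points) and baseline WM integrity on the overlapped regions between active vs. sham" groups, with an anticipated direction: "We expect to see a higher correlation between FC and WM in active group in later time points". For neuropsychiatric symptoms, a support vector regression will "examine the relationship between the sample's features (baseline WM tracts) and outcome", the outcome being change in NPI score, with no arm term described. This point concerns the circuit step, the only one of the two that compares arms.

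The circuit step names no arm × WM term, no FC change, no adjustment for baseline FC and no test for the difference between correlations. It does not say whether each correlation is taken across participants or across regions within a person. Elsewhere Section 17 does work with change in FC: Aim 1 (H1b) and H2b both use it.

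**The concern.** Whether a treatment effect depends on a baseline variable is a question of effect modification. In this trial it asks whether the active-minus-sham difference in FC varies with WM, that is, whether the slope of FC on WM differs between arms. The planned quantity is a correlation of FC level with WM in each arm. A correlation is a slope divided by total spread, so it can move because the spread of FC moved, or stay still while the slope changes. FC level at a later visit also carries stable differences between people that baseline FC could remove.

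At stake is the only planned arm comparison that bears on WM dependence of the circuit effect, in a pilot meant to inform a later trial. It could miss dependence that the same data would show or, in narrower circumstances, suggest dependence where there is none.

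**Working it through.** **The plan's own figure.** Section 17 sizes a single correlation with r² = 0.20 ("All of these calculations are based on power at 0.80 and alpha at 0.05"). By Fisher z, n = ((1.960 + 0.842)/atanh(√0.20))² + 3 = 36.9, so 37: it reproduces as a two-sided calculation. It covers one correlation in the whole sample, not a difference between two arms.

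**Inputs.** From Section 17: 40 participants and 10% attrition, so 40 × 0.90 = 36 completers. Assumed: 1:1 allocation (18 per arm), since the ratio is not stated; two-sided 0.05; correlation across participants; FC and WM in SD units.

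**Precision of the planned comparison.** SE of the difference in Fisher z = √(2/(18 − 3)) = 0.365. For 80% power the z difference must be 2.802 × 0.365 = 1.023, for example a correlation of 0.77 in one arm against 0 in the other. Power for 0.5 against 0 is 33%.

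**Model for the comparison** (all parameters assumed; the documents give none):
- FC_baseline = r·WM + e0
- FC_post = r·WM + e1 + arm·(0.5 + b·WM + h·u)
- e0 and e1 have variance 1 − r² and correlation φ; u is standard normal, unrelated to WM.

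Here b is the between-arm difference in slope, φ the residual pre-post FC correlation, and h the extra response variation in the active arm. The active-arm correlation is (r + b)/√((r + b)² + 1 − r² + h²); the sham correlation is r.

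**Why power depends on sign and on r** (h = 0):
- b = +0.8, r = 0: active 0.8/√1.64 = 0.625 against 0; z difference 0.73.
- b = +0.8, r = 0.7: active 1.5/√2.76 = 0.903 against 0.7; z difference 0.62. The correlation has little room to rise.
- b = −0.8, r = 0.7: active −0.1/√0.52 = −0.139 against 0.7; z difference 1.01. No ceiling applies.

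**Simulated power**, planned Fisher z on FC_post against the arm × WM test adjusted for FC_baseline (%; Monte Carlo error about 1 point):

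| b | φ | r = 0 | r = 0.3 | r = 0.5 | r = 0.7 | Loss (points) |
|---|---|---|---|---|---|---|
| +0.8 | 0.6 | 53 v 75 | 48 v 79 | 43 v 86 | 41 v 95 | 22 to 54 |
| +0.8 | 0.4 | 54 v 64 | 46 v 68 | 44 v 77 | 41 v 89 | 10 to 48 |
| +0.5 | 0.4 | 27 v 31 | 24 v 34 | 22 v 39 | 22 v 54 | 4 to 32 |
| −0.8 | 0.4 | 54 v 64 | 63 v 68 | 72 v 76 | 81 v 89 | 4 to 10 |
| −0.8 | 0.2 | 53 v 58 | 64 v 63 | 71 v 70 | 82 v 86 | about 0 to 5 |

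The total pre-post FC correlation is r² + (1 − r²)φ. The 54-point loss therefore assumes 0.49 + 0.51 × 0.6 = 0.80.

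**False positives (b = 0).** With h = 0 both arms have correlation r, the nulls coincide and both tests reject in about 5%. With h > 0 the active correlation falls to r/√(1 + h²). For h = 0.5, r = 0.8 gives 0.716 against 0.8, and the planned test rejects in about 5 to 8% over r = 0.3 to 0.8. For h = 1, r = 0.8 gives 0.566, and rejection is about 5% at r = 0.3, 11% at 0.6 and 24% at 0.8. The interaction test stays near 5% throughout.

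**Masking.** If slope and residual SD both double in the active arm (r = 0.7, b = 0.7), the active correlation stays at 0.7. The planned test rejects in 5%, the interaction test in about 40%.

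**Within-person reading.** If each participant contributes one FC–WM correlation across regions, the arm comparison asks whether tDCS changes coupling. None of the figures above apply, and it still does not ask whether the FC effect varies with WM.

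**The case against.** The strongest reply has four parts.

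*The sentence may mean within-person coupling.* The aim speaks of structural-functional coherence and of the overlapped regions, which fits that reading. This stands: the power and false-positive figures hold only for the across-participant reading. The mismatch between question and analysis remains on either.

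*The power loss is not general.* A reader might infer that the planned comparison always wastes much of the power. The documents do not support that: they give no FC reliability, no FC–WM correlation and no expected slope difference. The loss is nearly nil for negative dependence with low pre-post correlation, and about 4 points for b = +0.5 with φ = 0.4 and FC unrelated to WM. A slope difference of 0.8 is also large: with the assumed mean effect of 0.5, tDCS would lower FC in everyone more than 0.625 SD below the WM mean.

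*The nulls are often the same.* A reader might infer that the comparison tests the wrong null whatever happens. With equal residual FC spread in the two arms the nulls coincide, and false positives above 10% need both large added response variation and a strong FC–WM relation.

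*The expected higher correlation is not a decision rule.* A reader might infer that any numerically higher correlation in the active arm will count as dependence. Section 17 states an anticipated direction only, and a two-sided comparison would also pick up dependence the other way.

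Baseline may also be among the time points at which FC is correlated with WM, but no adjustment for it is specified.

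**Conclusion.** The point holds as a mismatch between question and analysis. Sections 1 and 17 ask about a WM-dependent treatment effect, and the planned circuit step does not estimate one directly on either reading of the correlation. The numerical cost is conditional: from about nothing to about 54 points of power under the stated assumptions, and false positives from about 5% to about 24%, the upper end needing added response variation of 1 SD and an FC–WM correlation of 0.8. The larger losses arise when dependence is positive, as it would be if the higher active-arm correlation the plan anticipates came from a steeper slope, and FC is stable over time or already related to WM. No primary or secondary conclusion rests on this step, so it is a worthwhile low-cost improvement to an exploratory analysis and not a threat to the trial's main results.

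**What to change.** For each pre-named LPG-circuit FC summary, fit FC_post = FC_baseline + arm + WM + arm × WM, or a mixed model over both post-baseline visits with the same terms plus visit. Report the arm × WM coefficient with its 95% CI as the exploratory answer to whether the effect depends on WM. Keep the FC–WM correlations by arm as description, and state whether they are taken across participants or within person.

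The cost is a few sentences in Section 17, with no new data: baseline DTI and FC are already collected. The downside is that the interaction stays imprecise at about 18 per arm. Power is only about 30 to 65% for a slope difference of 0.5, with residual pre-post correlation 0.4 to 0.6 and FC–WM correlation up to 0.7. It should therefore be reported as an estimate with its interval and labelled exploratory.

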Exploratory aim 2: Examine blood biomarkers at baseline for predicting cognitive and brain MRI biomarker responses to intervention. Blood neuropathological (amyloid beta [A β] 42, total tau [t-tau], and neurofilament light [NfL]) and neurotrophic biomarkers (brain-derived neurotrophic factor [BDNF], insulin growth factor-1 [IGF-1], and short-chain acylcarnitines [SCACs]) relate to cerebral amyloidosis, neurodegeneration¹⁷⁻¹⁹ and neurogenesis.^{20,21} Blood A β 42 may indicate cerebral amyloidosis,¹⁹ and blood t-tau, and NfL levels have been shown to reflect neurodegeneration across populations (older adults with AD, MCI, or normal cognition).^{17,18} Their blood levels also correlate with their cerebrospinal fluid (CSF) levels, as well as several neuroimaging biomarkers (amyloid plaques, AD-related brain atrophy, and brain hypometabolism).¹⁷⁻¹⁹ Decreased blood A β 42 and increased t-tau and NfL levels were also found in individuals with MCI or AD and were associated with cognitive decline and incident AD over time.¹⁷⁻¹⁹ Preliminary data from colleagues at the University of Minnesota demonstrated that increased baseline plasma t-tau levels correlated with greater cognitive decline in older adults with MCI over time.²² Moreover, plasma phosphorylated tau (p-tau) is a promising biomarker of neuronal injury. A recent study showed that plasma p-tau levels were better biomarkers for both acute and chronic traumatic brain injury than plasma t-tau levels alone - further providing evidence in support of blood biomarkers as surrogate endpoints for treatment responses in neurological conditions such as aMCI and AD.²³

Blood neurotrophic factors have been shown to cross the blood-brain barrier to increase hippocampal volume and memory.^{20,25-32} Higher plasma BDNF levels were linked to better memory, larger hippocampal volume, and reduced risk for AD.^{25,28,29} Whereas higher plasma IGF-1 levels were cross-sectionally associated with better cognition³³ and lower odds of AD,³⁴ longitudinal data have been inconsistent. However, a recent study showed that higher plasma levels of IGF binding protein-3 (IGFBP-3), which are essential for IGF-1 physiological action,³⁵ were associated with decreased risk for dementia.³⁰

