15. DATA AND SAMPLE STORAGE

Blood Specimen: Blood samples will be collected & processed at CRC. Full cryo boxes will then be transferred to 4W-156, -80 freezer in the SON until analysis is completed. **Blood Sample Data:** We will collect information on the following 8 biomarkers: A β 42, t-tau, p-tau, NfL, BDNF, IGF-1, APOE 4, and 2 SCACs [C0 and C5]. In addition, we will measure other blood-based biomarkers such as phospholipids. All data will be stored on an encrypted, password-protected database on the URMC server that is only available to study staff. Individual databases used to house identifying subject information (telephone number, address, date of birth) will also be stored on the URMC server, on a password-protected file management system, accessible only to study staff. Both databases will be managed by the UR information analyst on site. All datasets will be stored pursuant to IRB protocols.

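### Whether tDCS response differs by AD pathology is tested only through a positive/negative split with no marker or cut-off defined; a continuous marker-by-arm term would be a better test

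*Combined protocol and SAP*

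**What the plan says.** Section 1 sets the question as Exploratory aim 2: "Examine blood biomarkers at baseline for predicting cognitive and brain MRI biomarker responses to intervention". The aim speaks of blood levels that are raised or lowered and mentions no positive or negative status. Section 15 introduces the assays with "We will collect information on the following 8 biomarkers" and lists A-beta 42, t-tau, p-tau and NfL alongside neurotrophic and other markers, without thresholds.

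The blood analysis plan in Section 17 has two sentences. The first is: "We will compare AD pathology markers from blood with changes of NPS, cognitive measures, and MRI data using correlational analyses". The second is: "We will also examine if individuals with positive AD pathology respond differently to tDCS compared to those with negative AD pathology using ANOVA". The second names no outcome, no defining marker or combination of markers, and no cut-off or rule for setting one.

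**The concern.** The ANOVA needs each participant to be classed as positive or negative, while A-beta 42, t-tau, p-tau and NfL are described as levels. Two things follow. Cutting a continuous predictor in two usually costs power, and this study is small. And because the status is undefined, the analysis cannot be reproduced from the document, and the cut could be settled after outcomes are known.

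The correlations do not close the gap. A correlation of marker with change, pooled over arms, mixes prognosis with altered response to stimulation. Only a comparison between arms separates the two, and the ANOVA is the only blood analysis worded as one about response to tDCS. Since Section 17 says the results are meant to inform a future trial, a responder signal from an undefined split could misdirect that trial.

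**Working it through.** **Text check.** Exploratory aim 2 (Section 1), the blood-marker item under other measures (Section 4), the assay list (Section 15) and the blood analysis plan (Section 17) were read together. None defines positivity. The correlational sentence mentions neither arm nor interaction.

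**Inputs.** From Section 17: 40 participants, 10% attrition, alpha 0.05, power 0.80. Completers: 40 × 0.9 = 36. Assumed because the documents are silent: 1:1 allocation (18 per arm), a normal marker, a linear effect, and the size of the interaction.

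**The plan's nearest figure.** The blood analysis has no sample size of its own. Section 17 gives n = 37 for a correlation with r² = 0.20 between circuit and NPI-Q. By Fisher's z, two-sided: ((1.960 + 0.842)/atanh(√0.20))² + 3 = 36.9, so 37. This reproduces. As a benchmark, a correlation of that size at n = 36 has 79% power with the predictor continuous and 57% after a median split.

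**Information kept by a split.** For a normal marker with a linear effect, cut so that a proportion p lies on one side, relative efficiency is φ(z_p)²/(p(1−p)):
- 50/50: 0.3989²/0.25 = 0.637
- 30/70: 0.3477²/0.21 = 0.576
- 20/80: 0.2800²/0.16 = 0.490

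The sample size does not enter the formula. With 36 completers, a median split leaves 36/4 = 9 per arm-by-status cell. A 20/80 split leaves 18 × 0.2 = 3.6, about 4, in each smaller cell.

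**Power for the marker-by-arm interaction.** Simulated model: outcome = b × arm × marker + error, with arm coded ±0.5 and marker and error standard normal. Here b is the between-arm difference in slope, in residual SDs per marker SD. At 36 completers:

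| b | Continuous | Median split |
|---|---|---|
| 1.0 | 76% | 54% |
| 0.7 | 49% | 33% |
| 0.5 | 29% | 20% |

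Separate simulation runs at b = 1.0 gave 74–76% and 52–56%.

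**Other marker shapes.** For an equal mixture of two groups with means 2, 3 or 4 SD apart and a linear effect, a mid-point split keeps 68%, 75% or 81%. If response instead follows true class membership, it keeps about 93% at 2 SD and loses nothing at 3 SD or more.

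**Choosing the cut afterwards.** With no interaction present, one marker and one outcome, a median cut fixed in advance holds its level (5.1% at n = 36). Taking the best of three cuts gives roughly 11–13%. Taking the best cut over the central 60% of values gives 26–29%. These ranges span separate runs at 36 and 40 participants.

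**The case against.** A reader might infer that the blood plan throws away more than a third of the marker information on its 40 participants. The documents do not support that. The correlational analyses use the same markers with no split mentioned, and the ANOVA is introduced as an addition, so any loss is confined to one test. The one-third figure (1 − 0.637 = 36.3%) needs a normal marker and a linear effect, and the documents establish neither. It is also unrelated to the sample size. Speaking of positive and negative pathology is class language; if response really follows class, a well-placed cut may lose almost nothing. This part of the objection stands.

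A reader might also infer that the cut will be searched for. The plan permits this by silence but does not say it, so the inflated error rates describe possible conduct and not a planned procedure.

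Two further points stand. At modest interactions both versions are badly underpowered: at a slope of 0.5 the gain is 29 − 20 = 9 points. And a continuous test of every marker has its own multiplicity: four independent markers at 5% give 1 − 0.95⁴ = 18.5%. The fix must therefore name a principal marker.

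The core is untouched. The correlations are not described as arm-specific, and the missing definition matters even more if a class effect is what the investigators have in mind.

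**Conclusion.** The concern holds in a limited form. That the defining marker and cut-off are missing is a matter of text and needs no assumption. The power cost is conditional: for this one test it could range from near nil, with well-separated classes, to about half the information with a 20/80 split of a normal marker. The power contrasts rest further on 1:1 allocation, 36 completers and assumed slopes, of which 1 SD per SD is large. A cut fixed in advance costs power but keeps the error rate; only a cut chosen with outcomes in view inflates it. This is a low-severity point in an exploratory aim of a Stage 0 pilot, worth acting on because the better analysis is specific and cheap.

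**What to change.** In the blood analysis plan, make the test of differential response a regression of the outcome on arm, the continuous baseline marker (log-transformed where skewed) and their product, adjusted for the baseline value of the outcome. Report the interaction slope with its confidence interval. Name one principal marker and one principal outcome, and label the other markers as exploratory.

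If positive and negative groups are also shown, keep them descriptive, and fix the defining marker and cut-off before outcomes are examined by arm. Tie the date to that event and not to unblinding, because Section 4 lets data managers know the allocation throughout.

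The cost is a few sentences of SAP wording, with no new data or visits. The small downside is that the model assumes an approximately linear relation between marker and response, which should be stated and checked with a plot by arm.
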